6.3.2. Analyses of Demographics and Baseline Characteristics

Subject disposition (including reasons for early discontinuation), protocol deviations, demographics, baseline characteristics, medical history, will be presented descriptively.

Use of study drug and concomitant medications will also be presented descriptively.

6.3.3. Analyses of Safety Data

A descriptive analysis of the TEAEs, laboratory assessments, 12-lead ECG, and vital signs will be performed. Changes from baseline and shifts according to normal ranges will be presented as well.

Physical examination results will be listed only.

AEs will be fully described and coded according to the Medical Dictionary for Regulatory Activities Dictionary.

6.3.4. Pharmacokinetic Analyses

Descriptive statistics will be calculated for the plasma concentrations and PK parameters. Mean (\pm SE) concentration-time profile will be generated.

Individual subject GLPG1690 concentrations and PK parameters will be listed.

6.3.5. Pharmacodynamic Analyses

In blood, LPA C18:2 species peak area ratio will be used to calculate the percentage reduction versus baseline. Baseline will be the average of the predosing duplicates (predose sample from Day -1).

The percentage reduction from baseline will be calculated as follows:

% reduction = 100-(100 x visit/baseline).

Individual and mean percentage reduction from baseline over time plots will be generated.

The AUEC as well as E_{max} on Day 28 will be determined from individual effect time profiles.

PD marker percent reduction, AUECs and E_{max} will be compared between the treatment groups using an analysis of covariance (ANCOVA) model with the following covariates: disease severity (baseline FVC, baseline DLCO), age, gender, treatment group, country, and baseline value.

Within-group comparisons of PD marker level obtained on Day 28 at 1.5 h and 6 h post-dosing, and on Day 84, versus baseline will be investigated using a paired t-test

PD data will also be summarized descriptively per treatment and per time point.

The analysis will be performed for the LPA C18:2 species. Other LPA species might be analyzed if deemed appropriate.

In BALF, data for all LPA species detectable will be used for the analysis. LPA species peak area ratio will be used to calculate the percentage reduction versus baseline. Baseline will be the average of the predosing duplicates (predose sample from Day -1).

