EVENT	Visit 1 Screening	Visit 2 Baseline	DOSING PERIOD						EDV	FU
				Visit 3 ¹ W1	Visit 4 ¹ W2	Visit 5 ¹ W4	Visit 6 ¹ W8	Visit 7 ¹ W12		
Visit										
Study days (D)	D-28 to D-4	D-1	D1	D7 ±2 days	D14 ±2 days	D28 ±3 days	D56 ±3 days	D84 ±3 days		D98 ±3 days
PD blood samples ¹¹ (LPA)		X				X		X	X	X
Biomarker blood samples ¹²		X				X		X	X	X
BALF sample (bronchoscopy)		X						X	X ¹³	
Spirometry ¹⁴	X	X		X	X	X	X	X	X	X
Home-based spirometry		X	On a daily basis							
SGRQ		X				X		X	X	X
HRCT ¹⁵		X						X	X	
(S)AE assessment			Throughout the study							
Concomitant medications			Throughout the study							

AE=adverse event; BALF=bronchoalveolar lavage fluid; D=day; DLCO= diffusing capacity for the lungs for carbon monoxide; ECG=electrocardiogram; EDV=early discontinuation visit; EOS=end of study; FU=follow-up; FRI=functional respiratory imaging; FSH=follicle stimulating hormone; HRCT=high-resolution computed tomography; LPA=lysophosphatidic acid; PD=pharmacodynamics; PK=pharmacokinetic; SAE=serious adverse event; SGRQ=St George's Respiratory Questionnaire; SLB=surgical lung biopsy; W=week

¹¹ All PD samples will be taken predose. At Day 28, in addition to predose, samples will be taken 1.5 h and 6 h post dose

¹² All blood samples will be collected predose.

¹³ If feasible for the subject

¹⁴ All spirometry evaluations should be performed prior to administration of bronchodilator.

¹⁵ To measure FRI parameters. During the baseline visit an additional scan of the upper airway will be taken.

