2.4. BACKGROUND GLPG1690– CLINICAL DATA

To date, GLPG1690 (or placebo) has been administered in fed state to 40 healthy male subjects in a Phase I first-in-human (FIH) study (Study GLPG1690-CL-101). GLPG1690 (or placebo) was administered as a single oral suspension at a dose ranging from 20 mg to 1500 mg or a 300 mg capsule (Part 1 of the study). GLPG1690 (or placebo) was administered as a twice daily (*b.i.d.*) dose of 150 mg or a *q.d.* dose of 600 mg or 1000 mg for 14 days (Part 2 of the study).

Administration of single (up to 1500 mg) and multiple ascending oral doses of GLPG1690 (up to 1000 mg *q.d.*) for 14 days in healthy male subjects can be considered safe and well tolerated. No deaths, other serious adverse events (SAEs), or treatment-emergent adverse events (TEAEs) leading to study drug discontinuation have been reported. All TEAEs were at most moderate in severity. No clinically relevant abnormalities related to laboratory parameters, electrocardiogram (ECG), vital signs, or physical examinations were reported.

Single (up to 1500 mg) and multiple ascending oral doses of GLPG1690 (up to 1000 mg *q.d.*) for 14 days were assessed in healthy male subjects under fed conditions. GLPG1690 was rapidly absorbed with a median time to maximum plasma concentration (t_{\max}) of 0.5-2 h. The terminal half-life ($t_{1/2}$) after *q.d.* oral dosing for 14 days was 5.8 h. Steady-state exposure of GLPG1690 increased in proportion with the dose between 300 to 1000 mg total daily dose. Excretion of unchanged GLPG1690 in human urine was low (< 1.8% in 24 h) and rapid. There was no impact on the urinary 6 β -OH-cortisol/cortisol ratio after repeated dosing suggesting a lack of CYP3A4 induction by GLPG1690.

After a single administration of GLPG1690, a significant dose-dependent percentage reduction of LPA 18:2 was observed in plasma. This effect started from 0.5 h post dose, reached a plateau, and was sustained over time up to 24 h post dose. Multiple *q.d.* or *b.i.d.* ascending doses resulted in a similar effect on LPA 18:2. A strong reduction in LPA 18:2 levels was already observed at predose Day 14, pointing to a sustained effect over 14 days.

The effect on LPA 18:2 was also confirmed by area under the effect-time curve (AUEC) for the % reduction from baseline and maximum % reduction from baseline (E_{\max}).

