2.7. RATIONALE FOR THE CHOICE OF DOSE AND DOSING INTERVAL

A dose of 600 mg GLPG1690 administered *q.d.* has been selected to be evaluated for this phase IIa study.

Both preclinical and clinical study results were used to predict an efficacious dose. In the 21-day prophylactic BLM mouse model, GLPG1690's efficacy was reached (in terms of reduction of Ashcroft score) with AUC of 11 $\mu\text{g.h/mL}$, corresponding to 26 $\mu\text{g.h/mL}$ in humans after correction for plasma protein binding. Moreover, a GLPG1690 plasma concentration of 1 $\mu\text{g/mL}$ in healthy subjects allowed triggering maximum LPA 18:2 (PD) biomarker reduction (90%) which could be maintain over 24 hours with an AUC of 24 $\mu\text{g.h/mL}$. Both study results predict GLPG1690's efficacious dose to be around 220 mg.

A dose of 600 mg GLPG1690 *q.d.* is expected to be high enough to reach a plateau in the PD response in a population of subjects with IPF. In addition, 600 mg GLPG1690 is lower than the highest dose assessed in the FIH study in healthy subjects. In this study, administration of single (up to 1500 mg) and multiple ascending oral doses of GLPG1690 (up to 1000 mg *q.d.* for 14 days) in healthy male subjects was considered safe and well tolerated.

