3. STUDY OBJECTIVES

3.1. PRIMARY OBJECTIVES

- to evaluate the safety and tolerability of GLPG1690
- to characterize the PK and PD properties of GLPG1690

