4.3.3. Randomization

A total of approximately 24 subjects will be randomized in a 3:1 allocation ratio to active treatment with GLPG1690 or placebo.

Allocation of each subject to a given treatment will be described in a randomization list prepared by the CRO. This randomization list will be created using permuted blocks. Upon qualification for the study, subjects will be randomized using a computerized interactive voice/web response system (████████) to placebo or GLPG1690.

For each subject at each visit, the study center will contact the ██████████ system for the appropriate treatment number to be dispensed. Each medication kit will contain the relevant study drug for the period until the next visit.

Subjects and study personnel will be blinded to the treatment assignment. Additional details on blinding and unblinding are provided in Section 4.3.8.

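### Section 6.3.5 compares raw percent LPA reduction by standard ANCOVA at about 18:6; if log-scale variability is similar in both arms, nominal 95% intervals for the treatment difference cover about 73–88%

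*Protocol*

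**What the plan says.** Section 6.3.5 computes percent reduction in plasma LPA C18:2 as 100 − 100 × visit/baseline, where baseline is the mean of the duplicate Day −1 samples. Percent reduction, AUEC and E_max (the latter two on Day 28) "will be compared between the treatment groups using an analysis of covariance (ANCOVA) model with the following covariates": baseline FVC, baseline DLCO, age, gender, treatment, country and the baseline value. The section mentions neither a transformation nor unequal residual variances.

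Other sections that bear on this:

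- **Allocation (4.3.3):** "A total of approximately 24 subjects will be randomized in a 3:1 allocation ratio", which gives about 18 active and 6 placebo.
- **Expected effect (2.7 and 2.4):** section 2.7 cites a maximum LPA 18:2 reduction of 90% in healthy subjects and says the trial dose is "expected to be high enough to reach a plateau in the PD response". Section 2.4 adds that "A strong reduction in LPA 18:2 levels was already observed at predose Day 14".
- **Sampling (flow chart, footnote 11):** "At Day 28, in addition to predose, samples will be taken 1.5 h and 6 h post dose".
- **Status of PD (3.1):** a primary objective is "to characterize the PK and PD properties of GLPG1690". Section 6.1 justifies the sample size by the precision of the safety, PK and PD estimates.
- **Inference (6.3.1):** two-sided 5% level.

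**The concern.** Percent reduction cannot exceed 100. When LPA falls by most of its baseline value, active subjects are squeezed towards that ceiling, while placebo subjects keep the full spread of visit/baseline around 1. The arms then have very different variances, and the arm with the larger variance is the one with about 6 subjects. In that configuration a pooled variance understates the standard error, because the 18 low-variance subjects dominate the pool while the uncertainty of the difference comes almost entirely from the 6.

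At stake is how precisely the size of the PD effect is reported. Section 6.1 rests the sample size on that precision, and section 2.7 already used the size of LPA reduction to predict an efficacious dose. Detecting an effect is not at stake.

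**Working it through.** The protocol states no LPA SD, power or interval width, so there is no figure of its own to reproduce.

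**Inputs from the protocol.** N about 24 at 3:1, so 24 × 3/4 = 18 and 24 × 1/4 = 6; percent reduction = 100 − 100 × visit/baseline; the covariate list in 6.3.5; two-sided 5%; reductions of up to 90%.

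**Assumptions.** Visit/baseline is lognormal; within-subject log-SD 0.15–0.40; between-subject log-SD 0.4; three countries; baseline as the mean of duplicates, with independent or fully shared error.

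**Step 1: SD on the percent scale.** Let r be the fractional reduction. With the same log-SD in both arms, the SD of visit/baseline is proportional to its median, which is 1 on placebo and 1 − r on active. So active SD / placebo SD = 1 − r. The placebo SD is 1/0.5 = 2 times the active SD at 50% reduction and 1/0.1 = 10 times at 90%.

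**Step 2: pooled against true standard error.** Set the placebo SD to 1 and leave covariates aside.

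- Pooled SE = √{[(17(1 − r)² + 5)/22] × (1/18 + 1/6)}
- True SE = √{(1 − r)²/18 + 1/6}

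| Reduction | Pooled variance | Pooled SE | True SE | Ratio |
|---|---|---|---|---|
| 50% | (17 × 0.25 + 5)/22 = 0.420 | 0.306 | 0.425 | 0.72 |
| 70% | (17 × 0.09 + 5)/22 = 0.297 | 0.257 | 0.414 | 0.62 |
| 90% | (17 × 0.01 + 5)/22 = 0.235 | 0.229 | 0.409 | 0.56 |

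**Step 3: coverage with the planned model.** Simulation with 18/6 subjects, the full covariate list, three Day 28 time points (predose, 1.5 h, 6 h), AUEC over 0–6 h by trapezoid, and E_max as the largest reduction; 5,000 trials per cell. The target is the true difference in arithmetic means, and log-SD is equal in both arms.

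| Reduction | Percent reduction | AUEC | E_max |
|---|---|---|---|
| 50% | 87–88% | 87–88% | 87–89% |
| 70% | 80–83% | 80–83% | 80–83% |
| 90% | 73–77% | 73–76% | 74–77% |

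With treatment and baseline as the only terms, percent reduction covers 84–85%, 75–77% and 69–72%. With no treatment effect, coverage is 95% and type I error 4.7–5.1% for percent reduction. A separate simulation (6,000–8,000 trials per cell, log-SD 0.2–0.5, one to four countries, covariates unrelated to outcome) gave 86–88%, 79–83% and 72–77%. With 12:12 allocation it gave 92–95%, which shows that the damage comes from unequal variance combined with unequal allocation.

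**Step 4: if active subjects vary more on the log scale.** Coverage for percent reduction:

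| Reduction | Base log-SD | Extra 0.3 | Extra 0.6 | Extra 0.9 |
|---|---|---|---|---|
| 90% | 0.15 | 79% | 85% | 92% |
| 90% | 0.40 | 75% | 77% | 82% |
| 70% | 0.15 | 90% | 95% | 96% |
| 70% | 0.40 | 83% | 90% | 94% |

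With the active log-SD at twice placebo (0.50 against 0.25), coverage is 95% at 50% reduction, 91% at 70% and 78% at 90%.

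**Step 5: the alternatives.** ANCOVA on log(visit/baseline) with the same covariates covers 94.7–95.5% with equal log-SD, and 96–99% if active subjects vary more. A raw-scale model with group-specific residual variances and Satterthwaite degrees of freedom (about 5–6) covers 92–95% for percent reduction, AUEC and E_max (2,000 trials per cell). Its intervals are about 1.4 times (50% reduction) to 1.8 times (90%) as wide as the pooled ones. At 90% reduction and log-SD 0.15, for example, the median half-widths are 17.7 and 9.8 percentage points (17.7/9.8 = 1.8).

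**The case against.** The strongest reply is that the percent scale is not itself the fault: with group-specific variances it covers 92–95%, and 6.3.5 never says that one variance must be pooled. Section 6 defers detail to an SAP, which could add the variance structure without contradicting the protocol. That is true. But a plain ANCOVA is by default a common-variance model, and the protocol fixes both that model and the raw scale. A statistician who follows the text literally gets the short standard error.

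Second, 6.3.5 names no confidence interval for the difference. The test of no effect is valid, and the within-arm summaries and paired t-tests use each arm's own variance. This stands and limits the consequence to the between-arm estimate and its standard error. That estimate is still the placebo-controlled measure of a primary-objective effect.

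Third, equal log-SD is unproven. Differences in exposure and missed or late doses add variation only on active treatment. The Day 84 sample is predose, about 24/5.8 = 4 half-lives after the previous dose if that dose was on time, so the reduction there may be below 90%. This also stands: at 70% reduction or less, enough extra variation removes the problem. It does not near the plateau that section 2.7 expects. For placebo log-SD 0.3, equal raw SDs at a 90% reduction would need an active log-SD of about 1.5.

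Finally, percent reduction, AUEC and E_max were the first-in-human study's measures, and a geometric mean ratio is a different summary from an arithmetic mean. That is a real change, but the back-transformed result is still a percent reduction, and the raw values can be kept for display.

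**Conclusion.** The concern holds. Applied as written, the method understates the standard error of the treatment difference wherever LPA falls substantially. With equal log-SD the standard error is about 0.56 to 0.72 of its true value, and a nominal 95% interval covers about 73–88% for reductions from 90% down to 50%.

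The size is conditional, since the documents give no LPA SD. It shrinks if active subjects are more variable on the log scale, and it vanishes where the arms are alike, for example at Day 98 if the effect has washed out. At the 90% reduction the protocol cites, coverage stays at 75–85% even with extra active log-SD of 0.3–0.6. The conclusion that LPA falls is safe. This should be fixed because PD is a primary objective justified by precision and the correction is cheap; it does not threaten the trial's validity.

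**What to change.** In 6.3.5, carried into the SAP:

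1. Analyse log(visit/baseline) of the LPA C18:2 peak area ratio by ANCOVA, with log baseline as the baseline value and the other covariates unchanged. Report the geometric mean ratio with its confidence interval, back-transformed to percent reduction.
2. For AUEC, E_max and any comparison kept on the percent scale, fit group-specific residual variances with Satterthwaite-type degrees of freedom.
3. Keep raw percent reductions for plots and descriptive tables.

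The cost is wording, with no new data. There are two downsides: the raw-scale intervals lengthen by the factors given above, and the log-scale interval is somewhat conservative if active subjects are the more variable arm.

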6.3.6. Exploratory Efficacy Assessments

Exploratory endpoint data at each post-dosing visit will be analyzed descriptively. Comparison between GLPG1690 and the placebo group will be done exploratively.

Analysis methods:

- Continuous parameters will be analyzed using descriptive statistics of actual values, changes from baseline, and percent changes from baseline. GLPG1690 and placebo will be compared using an ANCOVA model on the changes from baseline, with the following covariates: disease severity (baseline FVC, baseline DLCO), age, gender, treatment group, country, and baseline value. Within-group comparisons of each visit versus baseline will be investigated using a paired t-test. For FRI parameters these analyses will be performed using a mixed effects ANCOVA model with subject as a random factor and the factors listed above as fixed factors.
- Missing data will be imputed, also for subjects who prematurely discontinue the study. The primary imputation method will be last-observation-carried-forward. An observed-case analysis will also be performed.
- Additional exploratory analyses and graphical presentations may be performed when deemed useful to better understand the data.

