Pulmonary function will be assessed using standard spirometry; FVC is currently the most commonly used and accepted endpoint in clinical studies investigating IPF treatments (Saketkoo, et al., 2014). Spirometry, or more specifically FVC reflects the burden of the IPF progress, and is relatively easy to measure and reproducible (Nathan & Meyer, 2014). However, since conventional pulmonary function tests such as spirometry have their limitations (*e.g.*, they cannot detect early signs of disease due to the compensatory behavior of healthy lung areas; in IPF, many spirometry endpoints remain normal even though the disease progresses) and since a study duration of 12 weeks may be considered too short to detect any differences in FVC, pulmonary function will also be assessed through high-resolution computed tomography (HRCT) scans used for generating functional respiratory imaging (FRI). FRI provides regional information about lung structure and allows for earlier demonstration of disease progression and/or therapeutic effects (De Backer, et al., 2015; Vos, et al., 2015). Furthermore, central reading of these images should reduce assessment bias.

In addition, change in the levels of a selection of biomarkers in blood and BALF (through bronchoscopy) will be assessed. Even though there currently are no validated biomarkers that track IPF progression or response to IPF treatment, a number of protein biomarkers have been shown to be increased in IPF (*e.g.*, ATX, Krebs von den Lungen 6/mucin type 1 [KL-6/Muc1], surfactant protein A (SP-A), chemokine motif ligand 18 [CCL18], surfactant protein D (SP-D), matrix metalloproteinase (MMP) 1, MMP7, intercellular adhesion molecule type 1 (ICAM1), vascular cell adhesion molecule type 1 (VCAM1), interleukin 8 (IL8), and S100 calcium-binding protein A12 (S100A12) (Greene, et al., 2002; Rosas, et al., 2008; Hara, et al., 2012; Kaminski, et al., 2012; Oikonomou, et al., 2012; Richards, et al., 2012; Jenkins & Goodwin, 2014; Nathan & Meyer, 2014) (Jenkins, et al., 2015). Change in a selection of biomarkers of disease activity will be evaluated in the current study. Results will help to refine our current understanding of the effect of GLPG1690 on IPF pathophysiology and will guide endpoint selection in future clinical studies.

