6.2.6. Intent to Treat Analysis Set

All randomized subjects who have at least one dose of study drug and have at least one post-baseline assessment with exploratory endpoint data.

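### LOCF as the primary imputation understates decline in a progressive disease, and for FRI and the exploratory BALF markers the wording does not rule out carrying baseline forward

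*Protocol*

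**What the plan says.** Section 6.3.6 sets the rule for the exploratory efficacy endpoints: "Missing data will be imputed, also for subjects who prematurely discontinue the study", then "The primary imputation method will be last-observation-carried-forward", then "An observed-case analysis will also be performed". The arms are compared by ANCOVA on change from baseline, and FRI gets a mixed-effects version with subject as a random factor. Within arms, "Within-group comparisons of each visit versus baseline will be investigated using a paired t-test".

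Change in FVC, in FRI parameters and in blood and BALF biomarkers are secondary objectives (Section 3.2). The flow chart (Section 1) schedules site spirometry at baseline, Weeks 1, 2, 4, 8 and 12, the early discontinuation visit (EDV) and follow-up. HRCT for FRI and bronchoscopy are scheduled only at baseline, Week 12 and the EDV, and the EDV lavage carries the condition "If feasible for the subject". Section 6.2.6 admits to the Intent to Treat set treated subjects who "have at least one post-baseline assessment with exploratory endpoint data", without requiring this endpoint by endpoint.

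**The concern.** LOCF assumes that nothing changes after the last value, whereas Section 2.1 describes progressive loss of lung function. Dropout may also depend on the outcome. Under Section 4.2.5, worsening that calls for another treatment approach is a mandatory reason for withdrawal, final evaluations after withdrawal are only encouraged, and subjects who stop drug are not replaced.

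Two things follow. An arm's mean decline is flattened whenever a declining subject leaves early, and this reaches the paired t-tests wherever imputed values are used. Second, FRI and the BALF markers have a single post-baseline time. A subject with early spirometry but no second scan or lavage is in the analysis set with only baseline to carry. Carrying it would enter a change of exactly zero as though it had been measured.

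The FRI case matters more than its share of the text suggests. Section 2.6 concedes that "a study duration of 12 weeks may be considered too short to detect any differences in FVC" and includes FRI because it "allows for earlier demonstration of disease progression and/or therapeutic effects". A trial with no formal sizing is read through its point estimates, and with about six placebo subjects one imputed value is a sixth of that arm's mean.

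**Working it through.** The protocol gives no decline rate, SD or dropout rate, so there is no stated figure to reproduce. From the protocol: about 24 subjects randomized 3:1 (Section 4.3.3), hence about 18 on GLPG1690 and 6 on placebo, and the visit weeks above. All mL and dropout figures below are assumptions.

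**1. Within an arm.** With linear decline, the share of the arm's 12-week decline lost is k/n × (1 − t/12), for k dropouts of n last seen at week t.
- 1 of 6, Week 8: 1/6 × 4/12 = 5.6%. Week 4: 1/6 × 8/12 = 11.1%.
- 2 of 6: 11.1% and 22.2%.
- For a decline of 50 to 100 mL this is about 3 to 11 mL (1 of 6) or 6 to 22 mL (2 of 6).

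If each subject's dropout probability is 5% to 20%, the chance of at least one placebo dropout is 1 − 0.95⁶ = 26% to 1 − 0.80⁶ = 74%.

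**2. Between arms.** Error in the difference (GLPG1690 minus placebo) = (ka/18 × Da − kp/6 × Dp) × (1 − t/12), where D is the 12-week decline, k the dropouts, and a and p the arms. A negative error makes GLPG1690 look worse than it is. Results in mL with last value at Week 4:

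| Decline placebo/active (mL) | kp of 6 | ka = 1 of 18 | ka = 3 of 18 | ka = 6 of 18 |
|---|---|---|---|---|
| 50/50 | 1 | −3.7 | 0 | +5.6 |
| 50/50 | 2 | −9.3 | −5.6 | 0 |
| 50/0 | 1 | −5.6 | −5.6 | −5.6 |
| 50/0 | 2 | −11.1 | −11.1 | −11.1 |
| 100/50 | 1 | −9.3 | −5.6 | 0 |
| 100/50 | 2 | −20.4 | −16.7 | −11.1 |

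The range is −20.4 to +5.6 mL, with 3 of 18 cells exactly zero. With last value at Week 8 every entry halves (−10.2 to +2.8 mL).

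**3. Against the precision available.** The 95% half-width is t(22) × SD × √(1/18 + 1/6) = 2.074 × SD × 0.471. For SD 100 to 250 mL this is 98 to 244 mL.

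**4. FRI and exploratory BALF markers, if baseline were carried.** If the other subjects' mean change is unaffected, the arm's mean change shrinks by k/n: 17% for 1 of 6, 33% for 2 of 6, 6% for 1 of 18 and 17% for 3 of 18. In BALF this concerns autotaxin and cell count (Section 5.7.2.3). BALF LPA is analysed under Section 6.3.5, which states no imputation.

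**5. Is a model on observed visits better?** Simulation: 18 versus 6 subjects, visits at Weeks 1, 2, 4, 8 and 12, linear decline, slope SD 80 mL per 12 weeks, visit error SD 60 mL, 1,000 trials per scenario. The model has random intercept and slope. LOCF and observed-case use ANCOVA on treatment and baseline only, without the other covariates in Section 6.3.6. The Monte Carlo standard error is about 2 mL.
- Random dropout after Week 4: LOCF error −5 to −16 mL, or +4 when only active subjects leave; model −2 to +1.
- EDV value obtained at Week 6: LOCF −6 to −13; model −1 to −4.
- Steepest Week 4 decliners leave: LOCF −6 to −8; observed-case −26 to 0; model −1 to −2.
- Steepest Week 8 decliners leave: all within about 2 mL.
- Root mean squared error: LOCF 53 to 55 mL; model 56 to 64; observed-case 57 to 72.

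**The case against.** **Baseline carry-forward is inferred.** This stands. No sentence orders it, and the SAP may limit carrying to post-baseline values. HRCT at the EDV has no feasibility condition, so only a subject who misses that scan is affected. A reader might infer that the plan instructs the analyst to impute zero change. It does not: it states a general rule and fails to exclude that result.

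**The observed-case analysis already covers FRI and BALF.** Largely true. With one post-baseline time it is close to the remedy proposed, provided EDV values count. What remains is which analysis is primary and one clarifying sentence. For FVC, observed-case is no safeguard: when steep decliners leave after Week 4, a separate simulation with true mean change −1.00 gave −0.87 to −0.74 for LOCF and −0.86 to −0.72 for observed-case.

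**FRI has its own mixed-effects model.** True, but the imputation rule does not exempt FRI, and any imputed value supplied to that model is treated as measured.

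**The alternative is not uniformly better.** This stands. Its root mean squared error is somewhat higher than that of LOCF. When the EDV captures a sudden late fall, LOCF gave +31 to +46 mL and the model +19 to +29 against a truth of +33 to +50.

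**The consequence is small.** This also stands. The comparisons are exploratory, Section 6.1 disclaims formal sizing, and the primary objectives are safety, PK and PD.

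**Conclusion.** The point holds at low severity. LOCF as the primary method conflicts with the protocol's own account of the disease. Under linear decline it removes 5.6% to 22.2% of the placebo arm's decline when one or two of six subjects are last seen at Weeks 8 to 4. An EDV value reduces the loss but does not remove it, because change from the EDV to Week 12 is still set to zero. For FRI and the exploratory BALF markers, the wording leaves open an imputed zero change worth 17% of the placebo mean change per subject.

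A reader might infer that LOCF tilts the FVC comparison towards GLPG1690 or could produce a false significant result. The documents do not support that. The error runs from about −20 to +6 mL under the assumed inputs, mostly against the active arm in those scenarios. It is zero with equal decline and equal dropout proportions, and always small beside the 98 to 244 mL half-width. Nor can it be said that LOCF alone hides acute deterioration. A fall that nobody measures is not recovered by a repeated-measures model either, and one captured at the EDV is well preserved by LOCF.

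The percentages rest on linear decline, and the mL figures on assumed declines, SDs and dropout counts, none of which the protocol supplies.

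**What to change.** In Section 6.3.6:

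- For endpoints with repeated post-baseline visits, make the main analysis a likelihood-based repeated-measures model on all observed site visits. Include treatment, visit, treatment-by-visit and baseline, and take within-arm changes from the same model. State how EDV values are assigned to a scheduled visit, for example the nearest, with ties going to the later one.
- Name the covariance. Random intercept and slope suits FVC: with the steepest decliners leaving, compound symmetry erred by −9 mL, against −6 for LOCF and −2 for intercept and slope. For SGRQ and blood biomarkers, scheduled on treatment only at Weeks 4 and 12, an unstructured 2 × 2 matrix is enough.
- Keep LOCF and observed-case as sensitivity analyses.
- For FRI and the exploratory BALF markers, make the observed Week 12/EDV analysis the main one and state that baseline is not carried forward.

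A further sensitivity analysis giving subjects withdrawn for worsening the worst observed change is optional.

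The cost is wording and slightly more programming, since all the data are already scheduled. The gain is less systematic error, not more precision. The model brings a somewhat larger root mean squared error than LOCF and more shrinkage of a late fall captured at the EDV, which is why LOCF should stay beside it.
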